4.1 Definitions

The following analysis population definitions apply to this study:

- **Screened:** All patients considered for participation in the study, whether or not they sign informed consent.
- **Screen Failure:** All screened patients who failed to meet inclusion criteria or met exclusion criteria. Patients can be screen failed for general or procedure criteria.
- **Enrolled:** All eligible patients who obtained informed consent, completed the index procedure, and have inclusion-exclusion criteria confirmed.
- **Intent-to-Treat (ITT):** All enrolled patients. The primary analysis, including all effectiveness, safety, and subgroup reporting, will be run on this population.
- **Completed:** All enrolled patients who completed the study follow-up or were known to have died prior to the follow-up.

5 Statistical Methods

Continuous variables will be summarized using the following descriptive statistics: N, Mean (SD), Median [IQR], Range (Min, Max). Categorical variables will be summarized using frequency counts and percentages of patients within each category. Confidence intervals will be reported for the following analyses only: effectiveness, safety, sensitivity, and change from baseline. Two-sided 95% confidence intervals will be reported using asymptotic intervals for continuous variables and Wald normal approximation binomial proportion intervals for categorical variables.

6 Baseline Characteristics

Baseline characteristics, including demographics, clinical characteristics, and angiographic characteristics, will be summarized using descriptive statistics for continuous variables and using frequency counts and percentages for categorical variables.

7 Patient Disposition

To summarize patient disposition outcomes, the number of patients in the following analysis populations will be recorded:

- Screen Failure
- Enrolled
- Intent-to-Treat (ITT)
- Completed

The number of patients who do not complete the study will be reported as well, broken down by their reasons for discontinuation.

8 Effectiveness Analysis

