16.4.10 Angiographic Outcome

The primary effectiveness endpoint is occlusion of the treated aneurysms. This is defined as the proportion of aneurysms with Class 1 and 2 occlusion as described by Roy et al (*Stroke 2001;32:1998-2004*):

- Class 1 – Complete occlusion
- Class 2 – Residual neck
- Class 3 – Residual aneurysm

Figure 3: Classification of Angiographic Results

Adopted from Roy, Milot and Raymond. Stroke 2001;32:1998-2004

STATISTICAL ANALYSIS PLAN

**SURF: A Prospective, Multicenter Study Assessing the Embolization of
Intracranial Aneurysms using WAVE™ Extra Soft coils, a part of the
Penumbra SMART COIL® System**

Protocol CLP 13669

Version 3.0

Contents

1	Overview	3
2	Sample Size	3
3	Interim Analysis	4
4	Analysis Populations	4
4.1	Definitions	4
5	Statistical Methods	4
6	Baseline Characteristics	5
7	Patient Disposition	5
8	Effectiveness Analysis	5
8.1	Primary Effectiveness Analysis	5
8.2	Secondary Effectiveness Analysis	6
8.3	Imaging Outcomes Analysis	7
8.4	Economic Analysis	7
8.5	Handling of Multiplicity	8
9	Subgroup Analysis	8
10	Safety Analysis	9
10.1	Primary Safety Analysis	9
10.2	Secondary Safety Analysis	9
10.3	Analysis of Adverse Events	10
10.4	Analysis of Deaths	10
11	Pooling Across Centers	10
12	Missing Data and Imputation Methods	11
13	Changes to Planned Analyses	11
14	References	12
15	Revision History	12

1 Overview

SURF is a postmarket, real-world, prospective, multicenter single-arm study. Its objective is to demonstrate the safety and efficacy of the Penumbra SMART COIL® System, including the WAVE™ Extra Soft Coils (WAVE) as a fill and finish coil, in the treatment of intracranial aneurysms. An independent core lab will read images to assess aneurysm occlusion rates, facilitating an analysis on the sensitivity and specificity of MRA imaging to detect residual aneurysm blood flow at final follow-up as compared to DSA (Section 8.3 of this document).

Approximately 800 patients will enroll at up to 60 global sites. Each site will be limited to a maximum enrollment of 120 patients (15% of total enrollment). An estimated 10% of enrolled patients will experience attrition by final follow-up.

This Statistical Analysis Plan (SAP) elaborates on statistical methods outlined in the study protocol and presents analysis conventions. The SAP will be signed off prior to database lock.

2 Sample Size

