8.5 Handling of Multiplicity

There will be no adjustment for multiplicity in SURF study reporting.

9 Subgroup Analysis

The following subgroup analyses will be performed for all primary and secondary effectiveness and safety endpoints using the ITT population:

- **Adjunctive technology used during treatment:** Balloon, Stent, Other, None
- **Age at time of informed consent (years):** < 65, \geq 65
- **Sex:** Female, Male
- **Ethnicity:** Hispanic or Latino, Not Hispanic or Latino
- **Race:** American Indian or Alaska Native, Asian, Black or African American, White, Other
- **Site country:** North America (US/Canada), Europe
- **Target aneurysm location:** Extradural ICA, ICA, ACA, MCA, Posterior Circulation, Other
- **Target aneurysm size:** Small (\leq 5 mm at its largest diameter), Medium (6 to 14 mm at its largest diameter), Large (15 to 24 mm at its largest diameter), Giant (\geq 25 mm at its largest diameter)
- **Target aneurysm status:** Ruptured, Unruptured
- **Target aneurysm anatomical location:** Bifurcation, Sidewall, Other
- **Neck width:** Small-Neck (< 4 mm Neck Width), Wide-Neck (\geq 4 mm Neck Width or Dome-to-Neck Ratio (defined as the maximum of dome width, depth, and height divided by neck width) $<$ 2)
- **Target aneurysm previously treated:** Previous Treatment at Admission, No Previous Treatment at Admission

Descriptive statistics and two-sided 95% Wald confidence intervals will be presented for each subgroup.

10 Safety Analysis

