10.1 Primary Safety Analysis

For the primary safety endpoints, frequency counts, percentages, and two-sided 95% Wald confidence intervals will be reported using the ITT population:

- **SAEs up to 24 hours post-procedure:** The percentage of patients who experience serious adverse event(s) with start date on the date of procedure (day 0) or the next calendar day.
- **Device-related SAE up to 7 days or discharge:** The percentage of patients who experience serious adverse event(s) with probable or definite relationship to the SMART Coil System from the date of procedure (day 0) through the date of discharge or seven calendar days from the date of procedure, whichever occurs earlier.

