10.2 Secondary Safety Analysis

For the secondary safety endpoints, frequency counts, percentages, and two-sided 95% Wald confidence intervals will be reported using the ITT population:

- **Major ipsilateral stroke:** The percentage of patients who experience major ipsilateral stroke adverse event(s), as defined in the SURF study protocol.
- **Device related SAE at final follow-up:** The percentage of patients who experience serious adverse event(s) with probable or definite relationships to the SMART Coil System from the date of procedure (day 0) through the final follow-up visit at 1 Year \pm 90 Days from the date of procedure.
- **All-cause morbidity and mortality:** The percentage of patients who experience either of the following events:
 - **All-cause morbidity:** mRS 3 to 5 at the final follow-up evaluation or worsening of mRS by 2+ points the date of procedure (day 0) through the final follow-up visit at 1 Year \pm 90 Days from the date of procedure. If the final follow-up mRS is missing, mRS as assessed at the 7-day and/or discharge visit will be substituted.
 - **All-cause mortality:** Death for any reason from the date of procedure (day 0) through calendar day 365

Adverse events occurring after the final follow-up visit at 1 Year \pm 90 Days and deaths occurring after day 365 will be separately tabulated and not included in endpoint and adverse event rates.

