10.4 Analysis of Deaths

Survival estimates will be used to evaluate the time-to-event using the Kaplan-Meier product-limit method for deaths through 365 days. With the date of procedure set at day 0, any event occurring on or before day 365 will be included. If clinical assessment is missing for a patient who has not died, the patient will be censored at the last follow-up date. Patients who are alive at day 365 will be censored at day 365. The time to death will be plotted with 95% confidence intervals.

Additionally, the frequency and percentage of deaths for any reason (all-cause mortality) will be presented with the two-sided 95% Wald confidence interval.

11 Pooling Across Centers

Analyses will be presented using data pooled across centers. The primary and secondary effectiveness and safety endpoints will be presented by study site to assess any potential site effects.

Pooling analyses will be conducted across study sites on the primary effectiveness and primary safety endpoints. Fisher's exact test (univariate analysis) and stepwise binary logistic regression

on study site, adjusted for key baseline and other appropriate variables (multivariate analysis), will be used. The multivariate results will take precedence in testing for site heterogeneity.

To assess the validity of pooling North America (US/Canada) and Europe sites, logistic regression models will be used for the primary effectiveness and primary safety endpoints. Stepwise multivariate binary logistic regression models with geographic location (North America (US/Canada versus Europe), study site, and a subset of key baseline and procedural predictors will be used for each primary endpoint to test for heterogeneity across geographic locations.

Wald odds ratios of the treatment effects for geographic location and study site will be presented with two-sided p-values to test whether the odds ratios equal 1. Centers enrolling three or fewer patients will be eliminated from all pooling analyses.

12 Missing Data and Imputation Methods

The primary analysis will be data as observed, in which results are reported using the data that are available without imputing missing values.

As sensitivity analyses, the primary effectiveness and primary safety endpoints will be recomputed using the ITT population after imputing missing data:

- Imputation using baseline scores (run for primary effectiveness only)

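### Wald intervals with no rule for zero or small counts will print 0%–0% or negative limits, and upper limits that are too low, for rare safety events in small subgroups; the full-sample primary intervals are little affected.

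*Combined protocol and SAP*

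**What the plan says.** SAP 5 limits where intervals appear ("Confidence intervals will be reported for the following analyses only: effectiveness, safety, sensitivity, and change from baseline") and fixes the method for proportions: "Wald normal approximation binomial proportion intervals for categorical variables". The endpoint sections repeat it:

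- SAP 8.1 and 8.2 name Wald for the effectiveness endpoints.
- SAP 10.1: "For the primary safety endpoints, frequency counts, percentages, and two-sided 95% Wald confidence intervals will be reported using the ITT population".
- SAP 10.2: "For the secondary safety endpoints, frequency counts, percentages, and two-sided 95% Wald confidence intervals will be reported using the ITT population".
- SAP 10.4, on the proportion of deaths: "will be presented with the two-sided 95% Wald confidence interval".
- SAP 9, for all primary and secondary endpoints: "Descriptive statistics and two-sided 95% Wald confidence intervals will be presented for each subgroup".

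SAP 11 adds site tables: "The primary and secondary effectiveness and safety endpoints will be presented by study site to assess any potential site effects". It does not say whether these carry intervals.

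Neither document gives an exact or score alternative, a rule for zero or 100% counts, truncation at 0 or 100%, or a minimum subgroup size. Two thresholds exist, but neither governs intervals: the 3% cut-off for adverse event categories (SAP 10.3) and the exclusion of centers with three or fewer patients from the pooling analyses (SAP 11). Protocol 10.8 to 10.10 ask for 95% intervals without naming a method.

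**The concern.** The Wald interval takes its width from the observed proportion. With no events the width is zero, and with few events the interval is too narrow and centered too low. Low-rate safety endpoints split into many subgroups are where this happens. SAP 9 lists 12 splits with 4+2+2+2+5+2+6+4+2+3+2+2 = 36 levels. With 5 primary and secondary safety endpoints, that makes 180 safety intervals.

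The error has a direction: the upper limit, the one a reader of a safety table looks at, is the one that is too low. A subgroup with no device-related SAE would appear to have a rate known to be exactly zero. The Kaplan-Meier limits for deaths (SAP 10.4), the site tests (SAP 11) and the best- and worst-case imputations (SAP 12) do not correct the interval printed beside a subgroup safety rate.

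**Working it through.** **Inputs.** From SAP 2: device-related SAE 22/800 = 2.75%; 24-hour SAE 71/800 = 8.875%; adequate occlusion 641/720, about 89%. From SAP 1: up to 60 sites, and "Each site will be limited to a maximum enrollment of 120 patients". From Protocol 1 (registry interim results): 31.0% of aneurysms ruptured, 0.2% giant, retreatment 6/157. The documents give no subgroup sizes, so n = 20, 50, 100, 173 and 200 below are assumed.

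**Formulas.** Wald: p ± 1.96·√(p(1−p)/n). Clopper-Pearson: beta quantiles; with zero events the upper limit is 1 − 0.025^(1/n). Coverage: the sum of binomial probabilities of all counts whose interval contains the true rate. P(zero events) = (1−p)^n.

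**The plan's own figures.** All 15 Wald intervals in the SAP 2 table reproduce to the stated rounding. At full sample:

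| Count | Wald | Clopper-Pearson | Wald coverage |
|---|---|---|---|
| 22/800 | 1.62–3.88% | 1.73–4.13% | 94.5% |
| 71/800 | 6.90–10.85% | 7.00–11.06% | 95.05% |
| 641/720 | 86.74–91.31% | 86.51–91.22% | 94.6% |

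No limit moves by more than about 0.25 points.

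**Small counts.**

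| Count | Wald | Clopper-Pearson |
|---|---|---|
| 0/2 | 0–0% | 0–84.2% |
| 0/20 | 0–0% | 0–16.8% |
| 0/50 | 0–0% | 0–7.1% |
| 1/50 | −1.88 to 5.88% | 0.05–10.65% |
| 3/97 | −0.35 to 6.54% | 0.64–8.77% |
| 3/800 | −0.05 to 0.80% | 0.08–1.09% |

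The lower limit is negative for 1, 2 and 3 events at every n from 14 to 800. Cutting output at 0 would hide this but would not change coverage.

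**Coverage at a true rate of 2.75%** (nominal 95%, with 2.5% in each tail):

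| n | Source of n | Wald coverage | Truth above upper limit | P(zero events) |
|---|---|---|---|---|
| 13 | mean per site, 800/60 | 30.4% | 69.6% | 69.6% |
| 20 | assumed | 42.7% | 57.3% | 57.3% |
| 50 | assumed | 75.0% | 24.8% | 24.8% |
| 100 | assumed | 93.7% | 6.2% | 6.2% |
| 120 | site cap | 83.9% | 15.5% | 3.5% |
| 173 | assumed | 85.4% | 14.3% | 0.8% |
| 200 | assumed | 91.1% | 8.5% | 0.4% |
| 248 | 31.0% of 800, if the registry mix holds | 90.2% | 8.9% | 0.1% |
| 400 | SAP 2 scenario | 91.6% | 7.6% | 0.0% |
| 800 | full sample | 94.5% | 4.6% | 0.0% |

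Coverage is not smooth in n. It is 94.7% at n=107 and 79.7% at n=108, because at n=108 the upper limit for a single event falls below 2.75%. Over n=150 to 400 the mean is 92.0% and the lowest value 85.4%, at n=173. The 0%–0% result is confined to small levels, but upper limits that are too low reach further.

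**Other rates.** For 24-hour SAE (8.875%), Wald coverage is 69.7% at n=13, 83.8% at n=20, 93.2% at n=50 and 95.1% at n=120. For retreatment at 6/157 = 3.8% with n=720, coverage is 93.3%, with the truth above the upper limit 5.4% of the time.

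**Giant aneurysms.** If the registry's 0.2% and its cut-off carry over, 800 × 0.002 = 1.6, about 2 patients. Zero device-related SAEs then occur with probability 0.9725² = 94.6%.

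**The case against.** The strongest case against is that little is at stake. Protocol 10.1 makes every analysis descriptive, there is no performance goal, the full-sample primary intervals are sound, and counts are printed beside the rates. This stands as a limit on severity. But in a descriptive study the estimates and their intervals are the product, and a 0%–0% interval beside 0/50 is still wrong.

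Second, the subgroup sizes are not in the documents. Splits by sex, age or rupture status may hold hundreds of patients, and the registry's size classes are not SURF's four. This also stands: the small-n figures are conditional. Yet coverage is still only 90.2% at n=248 and 91.6% at n=400.

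Third, n=13 and n=120 are site sizes, and SAP 11 does not ask for intervals by site. They are relevant only if SAP 5's general rule for safety analyses applies to those tables. The mean of 13 also assumes all 60 sites are used, and 120 is a cap.

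Fourth, single values of n can flatter or condemn the method, because coverage jumps. This is why the table includes n=100, where Wald does well, and why the mean over 150 to 400 is given.

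Fifth, 180 intervals overstates the number at risk. The 24-hour SAE and the composite of morbidity and mortality are not rare events, and they account for 2 × 36 = 72 of the 180. These are affected less, and 24-hour SAE mainly in small levels.

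**Conclusion.** The concern holds as a reporting defect that should be corrected. The SAP states a method, without a fallback, that gives wrong limits on foreseeable data. For device-related SAEs at 2.75%, true coverage is roughly 43% to 75% at n=20 to 50 and averages 92.0% over n=150 to 400, with most misses understating risk. A rare full-sample secondary safety endpoint could also be affected: 0/800 prints 0–0% against an exact upper limit of 0.46%.

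The conclusion does not extend to the full-sample primary intervals, and no trial decision changes. The coverage figures assume the SAP's planning rates; the subgroup sizes are assumed, or borrowed from the registry mix where marked.

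**What to change.** Revise the SAP before database lock; SAP 13 provides for this.

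- In SAP 5, 9, 10.1, 10.2 and 10.4, replace Wald with Clopper-Pearson for safety proportions, including deaths and all subgroup levels.
- For other subgroup proportions, and for rare secondary endpoints such as retreatment (SAP 8.2), name either Wilson or Clopper-Pearson.
- State whether the SAP 11 site tables carry intervals and, if so, apply the same rule.
- Changing the full-sample occlusion interval in SAP 8.1 is optional.
- Keep the SAP 2 table as the normal-approximation planning calculation, so that it still agrees with Protocol 10.2 and the synopsis. Add a sentence that reported intervals use another method.

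The protocol needs no change, and the programming is a different interval option in SAS. A fallback triggered only by small counts would remove the 0%–0% cases, but would leave the shortfall at n=248 or 400 unless its threshold were set high.

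The cost is conservatism. Clopper-Pearson coverage at 2.75% runs from 95.1% to 99.6% for n=20 to 800, so small-subgroup intervals widen and upper safety limits rise slightly. Planned precision holds at full sample: the half-width for 22/800 is 1.20 points against 1.13 under Wald (stated 1.5), and for 71/800 it is 2.03 against 1.97 (stated 2.5). In the smaller SAP 2 scenarios it does not always hold: 14/500 becomes 1.56 against a stated 1.5 (Wald 1.45). The 45/500 row becomes 2.61, but at 2.51 under Wald it is already just over its stated 2.5.

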8.1 Primary Effectiveness Analysis

For the primary effectiveness endpoint, frequency counts, percentages, and two-sided 95% Wald confidence intervals will be reported using the ITT population:

- **Adequate occlusion defined as Raymond-Roy Occlusion Class I and II at final follow-up:** The percentage of patients assessed as Raymond-Roy Class I or II out of patients who had a Raymond-Roy evaluation done (Class I, II, or III) at the time of final follow-up. Retreatments at final follow-up will be modelled as Raymond-Roy Class III.

The core lab data supersede the investigator-reported data in primary and secondary effectiveness analyses.

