10.2 Sample Size Estimation for the Primary Outcome

Approximately 800 patients will be enrolled in this post market study with estimated 10% attrition at final follow-up. Assuming an observed rate of 89% (641/720) for the endpoint of Raymond-Roy I-II at follow-up, the sample size precision is greater than $\pm 3\%$ for this endpoint (95% CI: 87% to 91%). Assuming an observed rate of 2.8% (22/800) for the primary endpoint of device-related serious adverse events up to 7 days or discharge, the sample size precision is greater than $\pm 1.5\%$ for this endpoint (95% CI: 1.6% to 3.9%). Assuming an observed rate of 8.9% (71/800) for the primary endpoint of serious adverse events at 24 hours post procedure, the sample size precision is greater than $\pm 2.5\%$ for this endpoint (95% CI: 6.9% to 10.9%). These precision estimates are based on the normal approximation binomial 95% confidence intervals and SMART Registry interim results (data on file at sponsor). Hence, the sample size provides an adequate level of precision for these primary endpoints.

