10.5.4 Completed

Completed subjects are all subjects who were enrolled and completed the study follow-up or were known to have died prior to the follow-up timepoint are considered completed. The completed subject metric will be provided for Final Follow-Up.

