Approximately 800 patients will enroll in this post-market study, resulting in 720 patients who achieve final follow-up after 10% anticipated attrition. This sample size provides adequate precision to estimate the primary effectiveness and safety endpoints.

Primary Endpoint	Assumption for Observed Rate ^[1]	95% CI ^[2]	Precision
Adequate occlusion defined as Raymond-Roy Occlusion Class I and II at final follow-up	89% (320/360)	86% to 92%	Greater than $\pm 3.5\%$
	89% (401/450)	86% to 92%	Greater than $\pm 3\%$
	89% (481/540)	86% to 92%	Greater than $\pm 3\%$
	89% (561/630)	87% to 91%	Greater than $\pm 3\%$
	89% (641/720)	87% to 91%	Greater than $\pm 3\%$
Device-related SAE up to 7 days or discharge	2.8% (11/400)	1.1% to 4.4%	Greater than $\pm 2\%$
	2.8% (14/500)	1.4% to 4.2%	Greater than $\pm 1.5\%$
	2.8% (17/600)	1.5% to 4.2%	Greater than $\pm 1.5\%$
	2.9% (20/700)	1.6% to 4.1%	Greater than $\pm 1.5\%$
	2.8% (22/800)	1.6% to 3.9%	Greater than $\pm 1.5\%$
SAEs within 24 hours post-procedure	9.0% (36/400)	6.2% to 11.8%	Greater than $\pm 3\%$
	9.0% (45/500)	6.5% to 11.5%	Greater than $\pm 2.5\%$
	8.8% (53/600)	6.6% to 11.1%	Greater than $\pm 2.5\%$
	8.9% (62/700)	6.8% to 11.0%	Greater than $\pm 2.5\%$
	8.9% (71/800)	6.9% to 10.9%	Greater than $\pm 2.5\%$

^[1] Set at SMART CLP 10023 Registry interim observed results (data on file at sponsor)

^[2] Two-sided 95% Wald normal approximation binomial proportion confidence interval

3 Interim Analysis

As there will be no interim analyses for the purpose of terminating the study early for success or futility, alpha adjustments will not be made to the confidence intervals in the final analysis. However, interim analysis may be performed for the purpose of publication or regulatory submission of SURF results.

4 Analysis Populations

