- Imputation using the worst clinical scenario, assuming the subject was assessed as Raymond-Roy Class III at the time of final follow-up (effectiveness) or experienced a primary safety event (safety)
- Imputation using the best clinical scenario, assuming the subject was assessed as Raymond-Roy Class I and II at the time of final follow-up (effectiveness) or did not experience a primary safety event (safety)

13 Changes to Planned Analyses

All changes to this Statistical Analysis Plan (SAP) will be documented in a revised SAP or the clinical study report.

14 References

Agresti A (2013). *Categorical data analysis*. John Wiley & Sons.

CLP SURF – SURF: A Prospective, Multicenter Study Assessing the Embolization of Neurovascular aneurysms using WAVE™ Extra Soft coils, a part of the Penumbra SMART COIL® System. 13669 protocol.

Meyers PM, et al (2010). Reporting standards for endovascular repair of saccular intracranial cerebral aneurysms. *American Journal of Neuroradiology*, 31(1), E12-E24.

CLP SMART – A prospective, multicenter registry assessing the embolization of neurovascular lesions using the Penumbra SMART COIL® System. 10023 protocol.

van Amerongen MJ, et al (2014). MRA versus DSA for follow-up of coiled intracranial aneurysms: a meta-analysis. *American Journal of Neuroradiology*, 35(9), 1655-1661.

Woodward K and Forsberg DA (2013). AngioSuite: an accurate method to calculate aneurysm volumes and packing densities. *Journal of Neurointerventional Surgery*, 5(Suppl 3), iii28-iii32.

15 Revision History

Version	Prepared By	Description of Changes
1.0	[name]	Initial Release
2.0	[name]	Updated number of sites, subgroup analysis, and pooling analysis to reflect global site enrollment under protocol revision C Updated sample size and endpoint definitions
3.0	[name]	Added sample size scenarios to Section 2. Sample Size

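### SAP 8.1 may drop known failures (early retreatment, or fatal rebleed of the target aneurysm) that have no final Raymond-Roy reading, and best-case imputation would score them as successes

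*Combined protocol and SAP*

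**What the plan says.** SAP 8.1 reports adequate occlusion in the ITT population as the share of patients in Class I or II "out of patients who had a Raymond-Roy evaluation done (Class I, II, or III) at the time of final follow-up". It then adds: "Retreatments at final follow-up will be modelled as Raymond-Roy Class III". SAP 8.2 uses the same denominator and the same retreatment sentence for Raymond I at final follow-up.

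Four other places bear on the point:

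- SAP 8.2 defines the retreatment rate by whether the target aneurysm was retreated since the index procedure, leaves out staged procedures, and divides by patients with an answer to that question. That is not the Raymond-Roy denominator.
- Protocol 6.9 leaves follow-up angiography to institutional standard of care. Footnote 5 of protocol Table 2 collects occlusion grading when a retreatment happens before the patient leaves the study.
- SAP 12 makes the primary analysis as observed. Its sensitivity analyses include a worst case (missing set to Class III) and a best case: "Imputation using the best clinical scenario, assuming the subject was assessed as Raymond-Roy Class I and II".
- Protocol 10.5.4 says that enrolled subjects who "were known to have died prior to the follow-up timepoint are considered completed". SAP 4.1 agrees. SAP 7 breaks down reasons only for patients who do not complete.

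No section says how a death before final imaging is counted in the efficacy endpoint.

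**The concern.** A retreated target aneurysm, or one that rebleeds fatally after the procedure, is a treatment failure known without any 1-year image. These are also patients who may well have no 1-year image. If entry to the denominator requires the image, failures can leave because they failed. The resulting error has one direction: it raises the occlusion rate.

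For retreatment the gap is one of wording. The Class III sentence assigns a class but does not waive the requirement that an evaluation was done, and no SAP rule says whether a grading taken at retreatment counts as the final follow-up evaluation. Two programmers could follow SAP 8.1 and obtain different denominators.

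For a fatal rebleed there is no rule at all. Because deaths are classed as completed, the disposition summary would not show that these patients are absent from the efficacy rate.

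At stake are the primary efficacy estimate and the upper sensitivity bound. Read literally, the best case counts a patient who died of a rebleed as adequately occluded.

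**Working it through.** **Inputs**

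- Enrolment is 800, "resulting in 720 patients who achieve final follow-up after 10% anticipated attrition" (SAP 2), so 800 × 0.90 = 720 and 80 patients have no final outcome.
- Planned rate: "Assuming an observed rate of 89% (641/720) for the endpoint of Raymond-Roy I-II at follow-up" (protocol 10.2).
- Interval: "Two-sided 95% Wald normal approximation binomial proportion confidence interval" (SAP 2, table footnote).
- The number of known failures without a reading, k, is not in the documents. I assume 8, 16 and 24, which are 1%, 2% and 3% of 800.

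**1. Reproduce the plan's figure**

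p = 641/720 = 89.03%. Half-width = 1.96 × √(0.8903 × 0.1097 / 720) = 2.28 points. The interval is 86.7% to 91.3%, which rounds to the stated 87% to 91%.

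**2. Restore k known failures to the denominator**

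Rate = 641 / (720 + k). This takes the 720 as all read and places the k patients among the 80 unread.

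| k | Share of 800 | Rate | 95% Wald interval | Fall from 89.03% |
|---|---|---|---|---|
| 8 | 1% | 641/728 = 88.0% | 85.7% to 90.4% | 0.98 points |
| 16 | 2% | 641/736 = 87.1% | 84.7% to 89.5% | 1.94 points |
| 24 | 3% | 641/744 = 86.2% | 83.7% to 88.6% | 2.87 points |

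The fall equals the half-width at about k = 19 (641/739 = 86.74%; 89.03 − 86.74 = 2.29 points), which is 19/800 = 2.4% of enrolment.

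If every retreated patient is scored Class III with or without a final reading, retreatment contributes nothing to k. Only unread fatal rebleeds remain.

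**3. The SAP 12 bounds**

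- Worst case: 641/800 = 80.1%. All 80 unread patients are failures, so known failures are included but cannot be told apart from ordinary loss to follow-up.
- Best case as written: (641 + 80)/800 = 721/800 = 90.1%. If 8 or 16 of the 80 are known failures, the best case consistent with the data is 713/800 = 89.1% or 705/800 = 88.1%.

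The as-observed 89.0% is the same whichever bound is reported beside it.

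**The case against.** The strongest objection concerns retreatment. Giving a patient Class III most naturally places that patient among those with a class. SAP 8.2 looks back to the index procedure when it defines retreatment, so a patient retreated at month 4 fits. Table 2 footnote 5 attaches a grading at retreatment to the final follow-up column. This largely stands. A reader might infer that retreated patients do leave the denominator and carry the SMART Registry rate into the sum: 800 × 6/157 ≈ 31, and 641/751 = 85.4%. The documents do not support that. It needs every retreated patient to lack a reading and the Class III rule to be ignored, and no section gives a fraction without a reading. What remains is that the evaluation condition is never expressly waived.

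Second, the worst-case analysis already counts every unread patient as a failure, and deaths appear in the morbidity and mortality endpoint (SAP 10.2) and the Kaplan-Meier analysis (SAP 10.4). Both are true. Neither changes the primary rate or repairs the best case.

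Third, how deaths count in an anatomical endpoint is a choice. A reader might want every death attributed to the target aneurysm scored as a failure. That is too broad: ruptured aneurysms are in scope, and a patient can die of the presenting haemorrhage with a well-occluded aneurysm. This objection stands and limits the rule to documented post-procedure rebleeds.

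Finally, protocol 10.1 makes all analyses descriptive. That lowers the stakes but does not remove a one-directional error from the headline figure.

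**Conclusion.** The point holds as a gap in the rules. Read literally, SAP 8.1 can omit a patient retreated early who has no final reading. It does omit a patient who dies of a target-aneurysm rebleed before imaging, and the best case in SAP 12 would score such unread patients as Class I or II.

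The documents do not show that retreated patients will in fact be dropped. The intent is plainly to count them as failures, and if the rule is applied to all of them their effect is zero. Otherwise the primary rate falls by about 1 point for each 1% of 800 patients restored: from 89.0% to 88.0% for 8 and 87.1% for 16, both within the 2.3-point half-width.

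These counts are assumptions. The documents give no rate of fatal rebleed. The registry's mortality after 24 hours, 11.4% (21/185), is not a substitute: it comes from a registry that also enrolled other lesion types and is not limited to target-aneurysm deaths. The effect is on an estimate and its interval; no test or performance goal is involved.

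**What to change.** In SAP 8.1, and for Raymond I at final follow-up in SAP 8.2, add:

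> Any ITT patient with retreatment of the target aneurysm at any time from the index procedure to final follow-up (staged procedures excluded), or with a documented post-procedure rebleed of the target aneurysm leading to death before final imaging, is included in the denominator as Class III whether or not a final image exists. Deaths from the presenting haemorrhage or other causes are not reclassified as failures and are reported by number.

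In SAP 12, restrict best-case imputation to patients with no known failure.

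The cost is two short edits before the SAP is signed off. No new data are needed: retreatment information (protocol 6.9), all deaths with a single cause (7.6.1) and relationship to the target aneurysm (7.6.2.2) are already collected. The rate may be slightly less favourable. Classification of a rebleed would rest on site assessment, because SAP 10.3 says there is no CEC; the report should say so.
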